9.4.5 Method of Assigning Subjects to Treatment Groups

Subjects who meet all eligibility criteria (refer to Section 9.3.1 and Section 9.3.2) may be enrolled into the study. Approval by the Medical Monitor will be required prior to enrollment of each study subject. Upon their enrollment into the study, subjects will be assigned a unique subject number.

Approximately 130 subjects will be enrolled at 6E13 vg/kg.

9.4.6 Selection of Dose Used in the Study

Data from an ongoing first in human study (Clinical Study 270-201) indicates that following single escalated doses of BMN 270 (6E12, 2E13, 4E13, 6E13 vg/kg), dose-related increases in FVIII activity were observed, with concurrent improvements in bleeding episodes and

Page 65

exogenous FVIII utilization, particularly at the 4E13 and 6E13 vg/kg dose levels. At all dose levels, BMN 270 is considered to be well-tolerated with mild increases in ALT as the most common adverse event. Please refer to the IB for detailed efficacy and safety data.

In order to further evaluate the dose-response relationship of BMN 270, subjects will be enrolled at a dose of 6E13 vg/kg. This dose is expected to be safe and effective based on clinical experience to date in 270-201. The DMC will review emerging safety and efficacy data and may recommend that a different dose (not to exceed 6E13 vg/kg) be administered. In such a case, up to 130 additional subjects may be enrolled at the new dose.

9.4.7 Blinding

This is an open-label study.

9.4.8 Prior and Concomitant Medications

All prescription and over-the-counter medications (including dietary and herbal supplements) taken by a subject for 30 days before Screening will be recorded on the designated eCRF. The Investigator may prescribe additional medications, deemed necessary to provide adequate prophylactic or supportive care, during the study, as long as the prescribed medication is not prohibited by the protocol. In the event of an emergency, any needed medications may be prescribed without prior approval, but the Medical Monitor must be notified of the use of any contraindicated medications immediately thereafter. Any concomitant medications added or discontinued during the study should be recorded on the eCRF. Medications should, whenever possible, not be recorded in the electronic database with a frequency of PRN.

The following medications are prohibited starting 30 days before Screening and through the end of the study, and the Sponsor must be notified if a subject receives any of these during the study:

- Any investigational therapy
- Systemic immunosuppressive agents, except for corticosteroids
- Emicizumab
- Fitusiran
- Concizumab
- Efavirenz
- Lamivudine

Page 66

The following medications should be avoided, starting 30 days prior to and for at least 52 weeks after BMN 270 infusion and minimized throughout the remaining duration of the study.

- Alcohol
- Herbal and natural remedies and dietary supplements
- Medications which may be hepatotoxic

Vaccines should also be avoided during this period, but in particular during the first 26 weeks unless clinically indicated.

The following medications should be avoided during oral corticosteroid therapy:

- Vaccines
- NSAIDs

9.4.8.1 Concomitant Hemophilia Treatments

Subjects on prophylactic FVIII therapy will discontinue their regular treatment regimen starting 4 weeks after the day of infusion and switch to an "on-demand" schedule. FVIII replacement therapy can always be taken as needed by the subject for treatment of an acute bleeding episode; the subject must carefully record his treatment and bleeding episodes in his diary. Prophylactic FVIII use can be used on a case-by-case basis and in consultation with the Medical Monitor to prevent bleeding in extenuating circumstances (eg, peri-operative).

In addition, information on FVIII usage and bleeding episodes by medical history must be well-documented and available and will be collected from subjects for the 12-month period immediately preceding study enrollment. Further information on the details that should be provided as part of the subject's well-documented medical and FVIII usage history are provided in the On Site File Binder.

In order to enable rigorous comparisons of pre-study versus on-study FVIII usage and bleeding episodes, the Medical Monitor will review each screened patient's prior bleed and hemophilia medication logs to determine if they are of "high-quality". Elements that will be assessed to judge the quality of such historical data may include, but are not limited to, the following:

- Date, type (eg, joint, muscle, other), location of bleeds
- Date, name, dose (calculated in IU/kg), and reason for use (eg, usual prophylaxis, one-time prophylaxis, treatment for bleed, surgery) of hemophilia medications.

Page 67

9.4.8.2 Therapeutic Glucocorticoid Treatment of Elevated Hepatic Transaminases

Therapeutic oral corticosteroids (prednisone or converted equivalent) should be initiated when either of the following occurs post-BMN 270 infusion in any subject and after consultation with the Medical Monitor (or their designee):

- ALT \geq 1.5x ULN or ALT > ULN & > 2x baseline value in 2 consecutive assessments within 72 hours and alternative etiologies have been ruled out, or ALT \geq 3x ULN in 2 consecutive assessments within 48 hours (refer to Table 9.8.8.3.2)
 - Whenever possible, a confirmatory lab draw for ALT should be performed, along with FVIII activity, prior to initiating oral corticosteroids.
 - Corticosteroids may be delayed if elevations in ALT are clearly not related to BMN 270 (eg, elevated ALT with concurrent increase in CPK due to intensive exercise)

The prescribed regimen for therapeutic oral corticosteroids is detailed in Table 9.1.6. Changes to the corticosteroid regimen should be made as follows:

Table 9.4.8.2.1: Adjustments to Corticosteroid Regimen

Tapering Corticosteroid Dose	Subject has been receiving oral corticosteroids <3 weeks Subject has been receiving oral corticosteroids ≥3 weeks	 Corticosteroids may be discontinued if: ALT < 1.5x ULN or ALT ≤ ULN & ≤2x baseline value; and FVIII levels > 20 IU/dL and within 10% of the pre-decline FVIII levels; and There is no concern for adrenal insufficiency post-withdrawal Corticosteroids may be tapered by 10 mg weekly if: ALT < 1.5x ULN or ALT ≤ ULN & ≤2x baseline value; and FVIII levels > 20 IU/dL and within 10% of the pre-decline FVIII levels; and There is no concern for adrenal insufficiency post-withdrawal
Increasing Corticosteroid Dose		reasing or FVIII level is decreasing while on oral corticosteroids, any rticosteroid dosing should be made only upon consultation with the

For any scenarios that are not accounted for in the above table, a discussion should take place between the Investigator and Medical Monitor regarding corticosteroid dose adjustments.

After discontinuation of oral corticosteroids, labs for ALT and FVIII levels will be measured once a week for 4 weeks to ensure stability in values.

Following initiation or completion of therapeutic oral corticosteroids, if ALT elevation $\geq 1.5 \text{x}$ ULN or ALT \geq ULN & $\geq 2 \text{x}$ baseline value is reported, corticosteroid management decisions will be based on discussions between the Investigator and Medical Monitor.

Page 68

Modification of the corticosteroid regimen may take into consideration possible confounders for the ALT elevation and impact on FVIII expression.

Management and monitoring of reactions to corticosteroids should be determined by the Investigator's clinical judgment in consultation with the Sponsor's Medical Monitor. This includes the contraindicated use of NSAIDs during corticosteroid treatment and specific monitoring not already covered by the schedule of events. The use of COX-2 inhibitors, while not contraindicated during corticosteroid treatment, should be limited, if possible. Practical management to prevent complications related to oral corticosteroid therapy may be undertaken at the discretion of the Investigator (eg, evaluation of glucose intolerance, hyperlipidemia etc.). Hepatitis B status and HCV viral load will be rechecked 6 weeks after the start of oral corticosteroid treatment and then 1 week and 13 weeks after the completion of oral corticosteroid treatment in subjects with a history of hepatitis B or hepatitis C. All adverse events (including any adverse events suspected to be caused by or related to corticosteroid use) should be reported as outlined in Section 10 of the protocol.

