PCR of vector DNA in blood, saliva, urine, semen, and stools ^d	X	X	X	X	X		X		X				X				X
Exploratory biomarker assessments ^e							X							X			X
Haemo-QOL-A assessment					X								X				
EQ-5D-5L					X								X				
HAL					X								X				

						Fol	llow-Up	After I	3MN 27	0 Infus	ion – W	eeks*					
	We	ek 1															
Assessment	D4	D8	2	3	4	5	6	7	8	9	10	11	12	13	14	15	16
Study Day*	4	8	15	22	29	36	43	50	57	64	71	78	85	92	99	106	113
WPAI+CIQ:HS					X								X				
PROBE					X								X				
AAV5 TAb Assay									X								X
AAV5 TI Assay									X								X
Testing for reactivation of hepatitis B and hepatitis C																	Xf
PBMC collection (for determination of AAV5 and FVIII specific immunity)			X		X		X		X		X		X		X		X
VWF:Ag														X			
Direct Thrombin Activity test ^e														X			

^{*} Visit windows are \pm 48 hours (and include the Day 4 visit).

^a Brief physical examination should be done at all weekly visits.

b Refer to Table 9.8.8.2.1 for laboratory assessments to be included, and to Table 9.8.8.3.1 for liver tests (LTs). LTs may be monitored more or less frequently (and in particular when ALT values are ≥1.5x ULN or > ULN & > 2x baseline value) based on discussion between the Medical Monitor and the Investigator and review of subject data, but LTs will be monitored at least twice weekly during periods when a subject's ALT is \geq 3x ULN. Subjects with ALT > 1.5x ULN or > ULN & > 2x baseline value during the study and either an alternative etiology considered or for further evaluation of the lab abnormality may undergo additional evaluations (eg, imaging studies including MRI or ultrasound, additional blood tests, and/or liver biopsy) at the discretion of the Investigator. Additional testing of FVIII and LTs during any study week may be performed if: (1) the ALT has increased to above ULN; (2) Increases in ALT values from prior assessment are accompanied by declines in FVIII activity level; or after a discussion between the Medical Monitor and the Investigator based on discussion between the Medical Monitor and the Investigator.

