g Subjects who meet the definition of treatment failure to BMN 270 therapy after Week 52 may omit the Q4W and Q6W visits during Years 2-5, and must attend only the Q12W and End of Year visits. Such subjects following the abbreviated schedule who have not yet cleared vector shedding in all fluids must still provide samples Q4W (during Year 2) or Q6W (during Years 3-5) until vector shedding has been cleared, either by reporting to the site to provide samples or by providing those samples to a MN professional.

Table 9.1.6: Schedule of Events – Therapeutic Corticosteroids for ALT Elevations

			St	eroid Trea	tment Peri	iod ^b				Pos	t-Steroid P	eriod ^c	
	Week 1	Week 2	Week 3	Week 4	Week 5	Week 6	Week 7	Week 8b	Week 1	Week 2	Week 3	Week 4	Week 13
Therapeutic corticosteroids (dose in mg/day) a	60 mg	60 mg	40 mg	40 mg	40 mg	30 mg	20 mg	10 mg					
FVIII activity testing									X	X	X	X	
Liver tests									X	X	X	X	
Hepatitis B testing ^d						X			X				X
HCV Viral Load ^d						X			X				X

^a Therapeutic oral corticosteroids may be initiated according to the parameters set out in Section 9.4.8.2.

b Following initiation or completion of steroid regimen, if a recurrence of ALT values ≥ 1.5x ULN or > ULN & > 2x baseline value is reported, steroid management decisions will based on discussions between the Investigator and Medical Monitor. Modification of the steroid regimen may take into consideration possible confounders for the ALT elevation, relationship between increases in ALT and FVIII activity, ALT/FVIII levels post steroid initiation, and adverse events related to steroid dosing. Guidance for tapering oral corticosteroid dosing can be found in Section 9.4.8.2.

^c After discontinuation of oral corticosteroids, weekly labs for ALT and FVIII levels will be measured once a week for 4 weeks to ensure stability in values. If these assessments are already being done as part of normal study follow-up, they do not need to be duplicated.

^d Should only be performed in subjects with a history of hepatitis B or hepatitis C prior to study entry.

Page 57

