9.8.8.3 Liver and Hepatitis Testing

Subjects will be screened for evidence of previous or active hepatitis B or hepatitis C infection at Screening; hepatitis B screening should include HBsAg, HBsAb, and HBcAb. Subjects with documented results showing an absence of active hepatitis B or hepatitis C infection (as measured by positive surface antigen for hepatitis B or positive RNA testing for hepatitis C) 30 days prior to providing signed informed consent do not need to repeat those tests during the screening period.

Evidence of ongoing hepatitis B or hepatitis C infection is exclusionary. Subjects with a history of hepatitis B or hepatitis C infection prior to study entry will be tested for hepatitis B and hepatitis C reactivation at Week 16. Subjects with a history of hepatitis B or hepatitis C will be asked for information about the treatments received as part of their medical history assessment at Screening.

Subjects with a previous history of hepatitis B or hepatitis C who receive therapeutic oral corticosteroids prior to Week 16 do not need to complete the Week 16 reactivation assessment; instead, they will be tested for hepatitis B and hepatitis C reactivation at the time points listed in Table 9.1.6.

A liver ultrasound and liver tests (LTs) during Screening will identify any significant hepatic dysfunction.

LTs will be monitored on a regular basis; at each time point, the following LTs should be assessed:

Page 76

Table 9.8.8.3.1: Liver Tests

Liver Tests (LTs)				
Alkaline Phosphatase	AST (SGOT)	Total Bilirubin	LDH	
ALT (SGPT)	Direct Bilirubin	GGT		

ALT, alanine aminotransferase; AST, aspartate aminotransferase; GGT, gamma-glutamyltransferase; LDH, lactate dehydrogenase; SGOT, serum glutamic-oxaloacetic transaminase; SGPT, serum glutamic-pyruvic transaminase

Elevated ALT levels (above the upper limit of normal range) should be evaluated according to the following plan:

Page 77

Table 9.8.8.3.2: Evaluation of ALT Elevations

ALT Level	Work-Up
Above ULN and <1.5x ULN	• Continue to monitor LTs and FVIII per protocol (repeat within 7 days if next protocol scheduled visit is >7 days from the time of the reported ALT elevation)
	 Consider evaluation to rule out alternative etiology (eg, concomitant medications, viral or autoimmune hepatitis, alcohol use, recreational drug use, special diets, strenuous exercise, prior and/or concurrent illnesses, exposure to environmental and/or industrial chemicals, etc.) (refer to Table 9.8.8.3.3)

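### The ALT clause added to the steroid stop/taper rule has no effect, and the lowest ALT band does not require the 72-hour repeat that its own start trigger needs

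*Protocol*

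**What the plan says.** All references are to the Amendment 3 text of the protocol.

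**Start.** Section 9.4.8.2 starts oral corticosteroids, after Medical Monitor consultation, on ALT at or above 1.5x ULN or on "ALT > ULN & > 2x baseline value in 2 consecutive assessments within 72 hours and alternative etiologies have been ruled out". A separate limb covers 3x ULN, with a 48-hour pair. On confirmation it says: "Whenever possible, a confirmatory lab draw for ALT should be performed, along with FVIII activity, prior to initiating oral corticosteroids".

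**Course.** "The prescribed regimen for therapeutic oral corticosteroids is detailed in Table 9.1.6". That table gives eight weekly doses: 60, 60, 40, 40, 40, 30, 20 and 10 mg/day.

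**Stop or taper.** Table 9.4.8.2.1 has two permissive rows. One allows discontinuation before 3 weeks; the other allows 10 mg weekly steps from 3 weeks on. Both use the ALT condition "ALT < 1.5x ULN or ALT ≤ ULN & ≤2x baseline value". Both also require FVIII above 20 IU/dL and within 10% of the pre-decline level, and no adrenal concern.

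**Discussion.** Further on, Section 9.4.8.2 covers ALT at or above 1.5x ULN, or at or above both ULN and 2x baseline, reported after initiation or completion. In that case "corticosteroid management decisions will be based on discussions between the Investigator and Medical Monitor". Table 9.1.6, footnote b, does the same "if a recurrence of ALT values ≥ 1.5x ULN or > ULN & > 2x baseline value is reported".

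**Retesting.** In Table 9.8.8.3.2 the row for ALT above ULN and below 1.5x ULN asks for monitoring per protocol, with this addition: "repeat within 7 days if next protocol scheduled visit is >7 days from the time of the reported ALT elevation". It then starts steroids on two consecutive values within 72 hours. The next two rows order their 72-hour and 48-hour repeats outright. The footnotes to the visit schedules allow liver tests more or less often, "in particular when ALT values are ≥1.5x ULN or > ULN & > 2x baseline value".

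**The concern.** The stop/taper condition should be the counterpart of the start condition. Amendment 2 had only ALT below 1.5x ULN in both taper rows. Amendment 3 added a lower start threshold and a clause in the taper rows that mirrors it. Joined by *or* to a wider condition, that clause removes nobody from the set allowed to stop. A subject can therefore start on the new trigger while the ALT part of the exit rule is already met.

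The retest point concerns the same trigger. It needs two values within 72 hours, but the row governing that ALT band does not order a second value in that time. Whether the confirming pair exists depends on discretionary testing.

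What is at stake is the correctness of two stated treatment rules for liver safety and preservation of transgene expression. The statistical analysis is not involved.

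**Working it through.** **1. The exit condition.** Write A for current ALT, B for baseline ALT and U for ULN.

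- Exit as written: A < 1.5U, or (A ≤ U and A ≤ 2B).
- A ≤ U implies A < 1.5U, so the bracket is a subset of the first limb.
- The exit therefore equals A < 1.5U.

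**2. The overlap with the new trigger.** The new trigger requires A > U and A > 2B. The values that meet both it and the exit are

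max(U, 2B) < A < 1.5U,

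which is non-empty when 2B < 1.5U, that is B < 0.75U. Eligibility allows B up to 1.25U. The protocol gives no ULN, so U = 40 U/L is assumed, in whole units:

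| Baseline ALT | Overlap (U/L) |
|---|---|
| 20 or lower | 41–59 |
| 25 | 51–59 |
| 28 | 57–59 |
| 30 or higher | none |

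When the starting pair straddles 1.5x ULN, the latest value decides. With baseline 20, a latest value of 56 meets the ALT part of the exit and 64 does not.

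**3. Grid check of the logic (not a frequency).** With U = 40, baseline 8–50 and ALT 5–200 there are 43 × 196 = 8,428 pairs.

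- The added clause changes the exit in 0 pairs.
- Pairs meeting both the new trigger and the exit: 13 × 19 + (17 + 15 + 13 + 11 + 9 + 7 + 5 + 3 + 1) = 247 + 81 = 328, all with baseline 8–29.
- All 328 also fall under the discussion sentence of Section 9.4.8.2.

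**4. What the optional exit allows, from the Table 9.1.6 doses.**

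- Full course: 14×60 + 21×40 + 7×30 + 7×20 + 7×10 = 2,100 mg over 56 days.
- Stop before 3 weeks, at the latest after 20 days: 14×60 + 6×40 = 1,080 mg (51%).
- Taper from Day 22: 14×60 + 7×40 + 7×30 + 7×20 + 7×10 = 1,540 mg over 42 days (73%), two weeks early.

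These figures describe the exit for anyone with ALT below 1.5x ULN who meets the other conditions. They bound what the overlap could lead to and do not measure the effect of the idle clause.

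**5. Retest interval.** The trigger needs two values within 72 h.

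- Weekly visits to Week 36, ±48 h: 168 ± 96 h, so 72–264 h. The pair is reached only when both windows are at their extremes.
- Two-weekly visits in Weeks 37–52, ±1 week: 336 ± 336 h, so nominally 336 h, with limits 0–672 h.
- The row's own limit, when the next visit is more than 7 days away: 168 h, and 168/72 = 2.3 times the interval the trigger allows.

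**The case against.** The strongest reply is that other provisions already cover the overlap. The discussion sentence includes every value in it. The table only permits stopping, so a site can follow both by discussing first, and the Medical Monitor was already consulted on the start. The default is to complete eight weeks. A decreasing FVIII level on steroids also calls for consultation. Elevations in this band are events of special interest, reportable within 24 hours.

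The taper wording also mirrors the start wording item by item. It could be meant respectively, with each exit applying to its own trigger.

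On retesting, the confirmatory draw and the footnotes make a 72-hour repeat possible. Table 9.1.4, footnote b, allows extra tests if ALT is above ULN or has risen by more than 10 U/L. Section 9.8.2.1 calls for liver tests every 72 hours after a sustained FVIII fall of more than 35% from peak. The amendment summary says the new criterion was added for flexibility.

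Most of this stands as a limit on harm, and it is why the point is minor. It does not give the clause a function. The table permits, on its ALT part, what a later sentence refers to discussion. The table's catch-all for scenarios it does not cover does not help, because read literally the table covers this one. The respective reading is plausible as intent, but it is not what the text says. The extra-testing provisions are optional, and the FVIII rule misses ALT rises without FVIII loss and can be deferred. None of them makes the 72-hour repeat a requirement for this band.

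**Conclusion.** Both points hold, as a minor correction to a safety rule. As written, the ALT condition in both taper rows is ALT < 1.5x ULN, and the clause added in Amendment 3 does nothing. For any baseline below 0.75x ULN there are ALT values that meet both the new start threshold and the ALT part of the exit. In the first row of Table 9.8.8.3.2, the new trigger depends on a second value that the row does not require in time.

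The logic rests on the text alone. The U/L bands rest on an assumed ULN of 40. The protocol does not say how many subjects have a baseline ALT low enough to be exposed, so no frequency can be given. No endpoint, estimate or error rate is affected.

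**What to change.** 1. In both taper rows, replace the ALT condition with *ALT < 1.5x ULN and not (ALT > ULN and > 2x baseline)*. This is the exact complement of the 1.5x ULN and new start thresholds: on the grid, no pair meets both and none meets neither. It only tightens the current rule, from 2,365 pairs allowed to 2,037 (2,365 − 328), and allows nothing that is now forbidden.

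   If the sponsor meant a stricter target for subjects started on the new trigger, namely ALT at or below both ULN and 2x baseline, the table should say that instead (1,392 pairs). The two differ: with ULN 40, baseline 10 and ALT 35, the first is met and the second is not.

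2. In the first row of Table 9.8.8.3.2, require liver tests and FVIII to be repeated no later than 72 hours after a value above both ULN and 2x baseline.

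The cost is two wording changes, a letter to sites, one extra ALT/FVIII draw per affected elevation, and possibly somewhat longer steroid courses.

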9.4.8.3 Monitoring of HIV-Positive Subjects

HIV-positive subjects who have previously enrolled in 270-301 should continue anti-retroviral therapy (ART) as prescribed and follow routine monitoring of CD4 count and viral load (US Dept Health Human Services, 2014). No alterations in the monitoring are indicated for enrolled immunocompetent HIV-positive subjects who receive corticosteroids as part of their enrollment in 270-301.

